2.14 Changes in the Conduct of the Study or Planned Analysis

The following changes as compared to descriptions in the CSP are described in this SAP:

- According to a sentence in the CSP, all patients' data is included in data listings. During SAP review it was decided to not include screening failure data in all data listings.
- The CSP planned to include statistical tests between time points. During SAP review it was decided to omit such tests due to small sample size.

3. OVERALL STUDY INFORMATION

The following information will be analyzed descriptively and corresponding details on the subject level will be provided in data listings:

- Patient overview
 - o Eligible patients
 - o Study populations
 - Screening completion / screening failures incl. reason
 - End of treatment incl. reason
 - End of study incl. reason for study end
- Attended visits

The following information will be provided only in data listings:

- Violated inclusion/ exclusion criteria
- Protocol deviations

4. BASELINE EVALUATION

Baseline characteristics will be summarized for ITT and PP Population, respectively.

4.1 Data Points

- Demographics and baseline characteristics (Age, gender, race, body weight and height, smoking status)
- Disease history
 - Cancer history
 - Histological type
 - Previous cancer treatment (any)
- Medical history by SOC and PT

The following information will be provided only in data listings:

- Concomitant medication
- Concomitant procedure

5. EFFICACY ANALYSIS

Efficacy analyses will be performed primarily on the PP Population and will be repeated on the the ITT population.

5.1 Data Points

Adapted from:

Following tables and figures will be provided:

- Tumor response at pre-surgery visit
 - o Overall response
 - \circ Δ tumor size
- Tumor regression grading stage (according to Junker criteria)
- Kaplan-Meier statistics for disease free survival (DFS)

Page 12 of 23

- Kaplan-Meier statistics for overall survival (OS)
- Tumor staging
- Tumor markers (CEA, Cyfra 21-1)
- Lung function
 - o forced expiratory pressure in 1 second (FEV1)
 - maximum vital capacity (VC MAX)
 - forced vital capacity (FVC)
 - inspiratory vital capacity (VC IN)
 - diffusion capacity of lung for CO (DLCO SB)
 - o diffusion capacity of lung for CO / alveolar volume (DLCO/VA)
 - o DLCOc SB
 - o DLCOc/VA
 - forced expiratory pressure in 1 second / maximum vital capacity (FEV1 % VC MAX)
 - partial pressure of 02 (p02)
 - partial pressure of CO2 (pCO2)

Corresponding details on the patient-level will be listed.

The following information will be provided only in data listings:

- Screening tumor assessment
- Target lesions
- Non-target lesions
- Translational research
- Survival status

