3.1 Treatment Phase

After screening, patients will be treated with Pembrolizumab every 3 weeks for 2 cycles. A non-invasive tumor assessment by PET-CT will be performed before neoadjuvant treatment and before curative intent surgery. If tumor progression or non-tolerable toxicity is noted during immunotherapy, an End of Treatment (EOT) visit will be performed and the patient will enter the follow-up phase.

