5.1 Study Assessments

5.1.1 Tumor assessments

All tumor evaluation is performed according to RECIST (Response Evaluation Criteria In Solid Tumors, V. 1.1, 2009, see Appendix 2 – RECIST 1.1 and table below) using CT scan or MRI scan. The baseline tumor assessment must be recorded and measured within 28 days prior to treatment start. The imaging technique for baseline tumor measurement(s) may be either computed tomography (CT, including spiral CT) or MRI according to investigator's choice and local routine standard of care. However, the same imaging technique must be used for all consecutive tumor assessments of the same patient. Whenever possible the same personnel should perform the tumor image evaluation.

All lesions identified at screening have to be assessed at each scheduled tumor measurement. Patients with measurable lesions will be eligible for inclusion. Measurable lesions must have at least one diameter of 20 mm with conventional techniques and at least 10 mm with spiral CT scan. Where there are several lesions, assessment is based on the sum of the longest diameters of the individual target lesions. Lymph nodes with a short axis of \geq 15 mm are considered measurable and assessable as target lesions. The short axis measurement should be included in the

sum of lesions in calculation of tumor response. Nodes that shrink to < 10 mm short axis are considered normal. All other pathological nodes (those with short axis \ge 10 mm but < 15 mm) should be considered non-target lesions.

In cases where there is suspicion of progression before the next scheduled assessment, an unscheduled tumor assessment should be performed.

Response Criteria

Definitions of the criteria used to determine objective tumor response/ Evaluation of target lesions:

Complete response	Disappearance of all target lesions. Any pathological lymph nodes (whether target or non-target) must have reduction in short axis to < 10 mm.
Partial response	At least a 30% decrease in the sum of diameters of target lesions, taking as reference the baseline sum diameters.
Stable disease	Neither sufficient shrinkage to qualify for PR nor sufficient increase to qualify for PD, taking as reference the smallest sum diameters on study (this includes the baseline sum if that is the smallest on study).

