Progressive disease	At least a 20% increase in the sum of diameters of target lesions, taking as reference the smallest sum on study (this includes the baseline sum if that is the smallest on study). In addition to the relative increase of 20%, the sum must also demonstrate an absolute increase of at least 5 mm. In the absence to clinical deterioration, a validation scan shall be performed after 4 weeks. Treatment continuation is warranted if tumor growth ≤20% of SLD. If PD is confirmed, the date of the pervious scan is counted as time point for PD. or Appearance of one or more new lesion. Note that the appearance of a single new lesion also requires validation of progression by another scan after 4 weeks.

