5.3 Removal of Patients from Treatment

Patients will be free to discontinue treatment or withdraw from the study at any time, for any reason, or they may be withdrawn/removed if necessary, to protect their health (see reasons for withdrawal below). It is understood by all concerned that an excessive rate of withdrawals can render the study uninterpretable; therefore, unnecessary withdrawal of patients should be avoided. Patients that will be withdrawn from the study will not be replaced.

Patients will be removed from further treatment for the following reasons:

- Disease progression
- Continued unacceptable toxicities despite optimal treatment or dose reduction
- During the treatment a delay of study treatment of more than 6 weeks
- Delay from screening to start of study treatment of more than 31 days
- Intercurrent illness, at the investigator's discretion
- Withdrawal of consent

- Non-compliance / Lost to follow-up
- Pregnancy
- Termination of the study by the sponsor

If there is a medical reason for withdrawal of treatment, the patient will remain under the supervision of the investigator until the AEs have been resolved or declined to baseline values.

If a patient has failed to attend scheduled assessments in the study, the investigator must determine the reasons and circumstances as completely and accurately as possible.

In case of premature discontinuation of the study treatment, the investigations scheduled for the EOT and the Follow-up visits should be performed, if possible. In any case, the eCRF section entitled "End of Treatment" must be completed.

Should a patient decide to withdraw, all efforts will be made to complete and report the observations as thoroughly as possible. The investigator should contact the patient to determine as completely as possible the reason for the withdrawal. A complete final evaluation at the time of the patient's withdrawal should be made with an explanation of why the patient is withdrawing from the study. If the reason for removal of a patient from the study is an adverse event or an abnormal laboratory test result, the principal specific event or test will be recorded on the eCRF.

If a patient withdraws consent for further study treatment, the patient should still be followed for progression and survival. If a patient withdraws consent for further participation in the study, follow-up assessments will be discontinued.

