2.8 Handling Missing Data

In general, missing data will not be imputed and analysis is restricted on available data, with the following exceptions:

- For time-to-event endpoints (DFS, OS), incomplete dates will be handled as described in Section 5.2.
- Response rates will consider missing response assessments as described in Section 5.2.
- Missing causality assessment for adverse events will lead to handling of the AE as related (see Section 7.3 . of the CSP)

2.9 **Protocol Deviations**

Potential protocol deviations will be collected prior to database snapshot for the main analysis. Potential protocol deviations will be discussed in a data review meeting (DRM) prior to database snapshot for the main analysis and will be classified as relevant or not relevant. A protocol deviation will be considered relevant if it has a potential influence on the efficacy analysis. Relevant protocol deviations will lead to exclusion from the PP Population. Relevant protocol deviations can be one of the following but are not limited to:

- at least one of the major inclusion criteria was not met (criteria with relevant impact on efficacy)
- at least one of the major exclusion criteria was fulfilled (criteria with relevant impact on efficacy) •
- administration of prohibited therapies during the screening and treatment phase as defined in the CSP •
- administration of no study treatment •
- no documentation of tumor assessment after start of study treatment •
- erroneous dose of study medication .

Medical Coding 2.10

All information regarding the medical coding of medical history and adverse events can be found in the coding guideline.

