7.1.3 Efficacy Analysis

| No | Legend | Content |
|--------|--------------------------------------|----------------------------------|
| 14.3.1 | Tumor Response at Pre-Surgery Visit | Overall response |
| | (PP Population) | Δ tumor size |
| 14.3.2 | Tumor Regression Grading Stage (PP | |
| | Population) | |
| 14.3.3 | Kaplan-Meier Statistics for Disease- | |
| | Free Survival (PP Population) | |
| 14.3.4 | Kaplan-Meier Statistics for Overall | |
| | Survival (PP Population) | |
| 14.3.5 | Tumor Staging (PP Population) | Tumor stage |
| 14.3.6 | Tumor Marker Values Over Time (PP | CEA |
| | Population) | Cyfra 21-1 |
| 14.3.7 | Tumor Marker Value's Change from | CEA |
| | Baseline (PP Population) | Cyfra 21-1 |

Confidential and intellectual property of Assign DMB. No part of this document or its contents may be duplicated, referenced, published or otherwise disclosed in any form or by any means without prior written consent of Assign DMB.

Page 19 of 23

| 14.3.8 | Lung function test results (PP | VC MAX |
|-----------|--|---------------|
| | Population) | FVC |
| | | VC IN |
| | | • FEV1 |
| | | FEV 1% VC MAX |
| | | DLCO SB |
| | | DLCO/VA |
| | | DLCOc SB |
| | | DLCOc/VA |
| | | • pC02 |
| | | • pO2 |
| 14.3.9-16 | Tables 14.3.1-8 will be repeated for the ITT Population. | |

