7.2.3 Efficacy Data

| No | Legend | Content |
|----------|---|---|
| 16.2.3.1 | Screening Tumor Assessment (ITT Population) | Patient ID, Visit, Date of assessment, Number of |
| | | target lesions, Current sum LD [mm], Current |
| | | sum LD present, Number of non-target lesions, |
| 16.2.3.2 | Tumor Response at Pre-Surgery Visit (ITT | Patient ID, date of assessment, Any new |
| | Population) | lesions, New lesion location, New lesion |
| | | present, Date of progression, Current sum LD |
| | | [mm], current sum LD present, Baseline sum |
| | | LD [IIIII], A lumor size, Target lesion response |
| | | Reason inconsistent (TL response) Non-target |
| | | lesion response. Non-target lesion response |
| | | present. Overall response calculated. Overall |
| | | response investigator. Reason inconsistent (OA |
| | | response) |
| 16.2.3.3 | Target Lesion Details (ITT Population) | Patient ID, Visit, Target lesion, Location, |
| | | Description of location, Method, Diameter [mm], |
| | | Lesion present, Lesion too small to measure, |
| | | Lesion diameter (calculated) [mm] |
| 16.2.3.4 | Non-Target Lesion Details (ITT Population) | Patient ID, Visit, Non-Target lesion(s), Location, |
| | | Number of lesion(s), Description of location, |
| | | Method, Lesion(s) still present, Lesion(s) not |
| 16235 | Histology (ITT Population) | ASSESSED Patient ID. Tumor regression grading performed |
| 10.2.3.3 | | Date tumor regression grading Regression |
| | | grading stage Reason regression grading not |
| | | performed. Tumor size (largest diameter) [mm]. |
| | | Histologic subtype, Adenocarcinoma subtype |
| 16.2.3.6 | Overall Response (ITT Population) | Patient ID, OS [months], OS censored, DFS |
| | | [months], DFS censored |
| 16.2.3.7 | Tumor Staging (ITT Population) | Patient ID, Visit, Stage identifier, Stage |
| 16.2.3.8 | Tumor Markers (ITT Population) | Patient ID, Visit, Has blood sample been drawn, |
| | | Date of sample drawn, Actual age [years], |
| | | Parameter, Value, Unit, Clinically relevant, |
| 40.0.0.0 | Lung Function (ITT Deputching) | Causal relationship |
| 10.2.3.9 | Lung Function (III Population) | Patient ID, VISIT, Lung Tunction test, Test |
| | | Parameter (Rest) Value Unit ((Rest) value) |
| | | Rest/target value [%] |
| 16.2.3.9 | Lung Function (ITT Population) | Causal relationship Patient ID, Visit, Lung function test, Test performed, Date test performed, Method, Parameter, (Best) Value, Unit ((Best) value), Best/target value [%] |

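### Progression documented on an unscheduled scan before the pre-surgery visit is counted as PD in no efficacy table, because the SAP ties RECIST response to that visit alone

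*SAP*

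**What the plan says.** **Response analysis.** SAP 5.1 lists "Tumor response at pre-surgery visit", comprising overall response and Δ tumor size. SAP 7.1.3 titles Table 14.3.1 "Tumor Response at Pre-Surgery Visit" for the PP population; Table 14.3.9 is its ITT repeat. Listing 16.2.3.2 in SAP 7.2.3 carries the same title and has no visit column.

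**Scans and patient path.** Protocol 5.1.1 states: "In cases where there is suspicion of progression before the next scheduled assessment, an unscheduled tumor assessment should be performed". Protocol 3.1 states: "If tumor progression or non-tolerable toxicity is noted during immunotherapy, an End of Treatment (EOT) visit will be performed", after which the patient enters follow-up. For premature discontinuation, protocol 5.3 says that "the investigations scheduled for the EOT and the Follow-up visits should be performed, if possible". The schedule of assessments places tumor assessment at screening and at the pre-surgery visit (day 43-50), and none at EOT.

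**Confirmation.** Under protocol 5.1.1, if there is no clinical deterioration, "a validation scan shall be performed after 4 weeks"; once confirmed, PD is dated to the earlier scan.

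**Missing responses.** SAP 2.8 says: "Response rates will consider missing response assessments as described in Section 5.2". SAP 5.2 defines DFS, OS, the handling of incomplete dates and Δ tumor size. It contains no rule for missing response.

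**The concern.** Tumor response is one of the primary endpoints. The patients most likely to have no pre-surgery assessment are those whose tumor has already grown. If the response table holds only what was recorded at that visit, documented progressions fall outside it, and the error favors the treatment.

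It matters here because protocol 1.3.1 names tumor progression as a route to inoperability, and protocol 1.4 names surgical delay, with the tumor possibly becoming unresectable, as the general risk of the strategy. A reader of the efficacy tables would want to see how many patients progressed while waiting for surgery.

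**Working it through.** **Step 1. Follow one patient.** Progression is suspected after the first dose, an unscheduled scan shows it, and the patient goes to EOT before day 43.

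| Output | Does the progression appear? |
|---|---|
| Tables 14.3.1 / 14.3.9, response | No: tied to a visit the patient does not have |
| Table 14.3.2, regression grading | No: needs resected tumor |
| Tables 14.3.3 and 14.3.4, DFS and OS | No: both start at surgery and are not calculated without a surgery date (SAP 5.2) |
| Tables 14.3.5 to 14.3.8, staging, markers, lung function | No: they do not report progression |
| PP population (protocol 8.3.2, SAP 2.9) | The scan counts as a tumor assessment after treatment start, so this criterion is met |

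The same scan thus helps to qualify the patient for the primary efficacy population while its result is left out of the response table.

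**Step 2. Who is affected.** Where a validation scan is needed, it comes 28 days after the first. It falls inside the day 43-50 window if the first scan was between day 43 − 28 = 15 and day 50 − 28 = 22. A scan at the nominal day 21 is validated on day 49. Some progressors may therefore still be captured at the pre-surgery visit. The gap is mainly for patients sent to EOT before it.

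**Step 3. The plan's own reference figure.** Protocol Table 3 gives a 10% radiologic response rate with an exact 95% interval of 2.1 to 26.5 at N = 30. With x = 3 and n = 30, the Clopper-Pearson limits are the 2.5% quantile of Beta(3, 28) and the 97.5% quantile of Beta(4, 27), that is 2.1% and 26.5%. The figure reproduces and is not disputed.

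**Step 4. Size.** The documents give no early-progression rate. Assume k = 1 to 4 early progressors without a pre-surgery visit, 30 patients in the analysis population, 3 responders, and no PD at the pre-surgery visit itself.

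- Response rate on non-missing data: 3/(30 − k). On all patients: 3/30.
- PD rate as tabulated: 0. With early progression counted: k/30.

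| k | Response, non-missing | Response, all 30 | PD as tabulated | PD with early progression (95% CI) |
|---|---|---|---|---|
| 1 | 3/29 = 10.3% | 10.0% | 0% | 1/30 = 3.3% (0.1 to 17.2) |
| 2 | 3/28 = 10.7% | 10.0% | 0% | 2/30 = 6.7% (0.8 to 22.1) |
| 3 | 3/27 = 11.1% | 10.0% | 0% | 3/30 = 10.0% (2.1 to 26.5) |
| 4 | 3/26 = 11.5% | 10.0% | 0% | 4/30 = 13.3% (3.8 to 30.7) |

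If 2 further patients show PD at the pre-surgery visit, k = 4 gives 2/26 = 7.7% as tabulated on non-missing data, against 6/30 = 20.0%. The shortfall is 12.3 points, so it depends little on that assumption.

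**Step 5. Is it likely to arise at all?** The chance of at least one such patient among 30 is 1 − (1 − p)^30. For assumed rates p of 3%, 5% and 10% this is 60%, 79% and 96%.

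**The case against.** Several counter-arguments carry weight.

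- **The data are not lost.** A reader might infer that early progression disappears from the report. The documents do not support that. Listings 16.2.3.3 and 16.2.3.4 have a visit column and no visit restriction, and SAP 2.12 promises all recorded data of eligible patients in listings. SAP 3 plans a descriptive summary of end-of-treatment reasons, and disease progression heads the removal reasons in protocol 5.3. Patients who miss surgery also count toward the stopping rule in protocol 5.4. This stands, with one caveat: the contents given for Table 14.1.1 name only end of study. What is missing is the count as PD in an efficacy table.
- **The response rate is not shown to be inflated.** One might read SAP 2.5 (non-missing observations) as fixing the base at 3/26. But SAP 2.8 announces an exception for response rates, so the base is undefined. The shift is 1.5 points at k = 4, against a planned interval of 2.1 to 26.5.
- **Protocol 1.4 does not name progression as the main risk.** It names delay of surgery and resulting unresectability. Progression as a cause of inoperability is in 1.3.1.
- **The validation scan narrows the group.** This stands, as step 2 of the working shows.
- **The eCRF may accept unscheduled scans.** Possibly; it is not available. The SAP gives no instruction to use them.
- **Protocol 8.4.3 specifies baseline and pre-surgery imaging.** It does, but it does not say how to class a patient whose progression is documented earlier and who never has the second scan.
- **The trial is descriptive, and no PD rate is a named endpoint.** True. PD is nevertheless one category of the overall response that the table reports.

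**Conclusion.** The gap is real but limited. As written, a patient with progression on an unscheduled scan who goes to EOT before the pre-surgery visit is not counted as PD in any efficacy table, and the rule that should cover missing responses is announced in SAP 2.8 but absent from SAP 5.2. The main distortion is in the PD rate: 3.3 to 13.3 percentage points too low if 1 to 4 of 30 patients are affected. That range is an assumption, and the true size is unknown. The effect on the response rate is small and depends on the denominator. The conclusion rests on the SAP text being applied literally; an eCRF page that takes unscheduled scans could soften it. It should be corrected, because the omission runs in the treatment's favor within a primary endpoint and the scans are already required.

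**What to change.** In SAP 5.2, add the rule that SAP 2.8 refers to:

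1. Define overall response from all RECIST assessments after the first dose and before surgery or EOT, scheduled or unscheduled.
2. Count progression documented at any of them, under the existing definition in protocol 5.1.1, as PD. State how a first scan without a validation scan is classed.
3. Show not evaluable as its own row, and keep every patient of the analysis population in the denominator.
4. Report how many PDs came from unscheduled scans.
5. Retitle Tables 14.3.1 and 14.3.9 and Listing 16.2.3.2 to match.

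Δ tumor size can stay at the pre-surgery visit, and Listings 16.2.3.3 and 16.2.3.4 need no change. The cost is SAP wording and minor programming, with no new scans and no change to patient management. The downside is a reported PD or response rate that may look slightly less favorable.

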8.2 Sample Size Calculation

A phase II approach will be used to generate preliminary hypothesis generating data. No formal sample size estimation has been performed. The scope is to gather information on feasibility, safety and efficacy.

Target sample size is N=30

The rationale for the sample size of this trial is based on ethical, clinical as well as scientific considerations. The neo-adjuvant treatment approach with an immune check-point inhibitor is highly experimental with only limited data on safety and feasibility available. Therefore, only a small number of patients should be subjected to this experimental treatment. Nevertheless, the sample size should allow the generation of statistically meaningful evidence for feasibility and safety to permit the decision to further develop this treatment approach.

With a sample size of N=30 and assuming that the number of events follows a binomial distribution B(30,p), events with an incidence rate p > 9.5% will be observed at least once with a 95% probability. This observation limit will exclude individual pembrolizumab related SAEs but covers most of the historical reference events/rates of the primary endpoints in this trial as well as the early stopping rule.

The degree of the potential evidence provided by a sample size of N=30 is summarized in Table 3.

Table 3 Reported reference data and exact CI under a sample size of N=30 [Clopper Pearson
method] [13-15]

Adverse event / endpoint	Reported Frequency	95% CI for sample size of N=30
AE rate in Pembrolizumab monotherapy	97.4%	83.9 - 100.0
trials		
Drug related AE rate in Pembrolizumab	73.7%	54.5 - 88.0
monotherapy trials *		
SAE rate in Pembrolizumab monotherapy	37.2%	20.4 - 56.7
trials *		
Drug related SAE rate in Pembrolizumab	10 %	2.1 – 26.5
monotherapy trials *		
Cumulative rate of the 5 most frequent	9.4%	1.8 – 25.7
SAEs in Pembrolizumab monotherapy		
trials and potential impact on neo-adjuvant		
treatment approach and/or surgery		
[pneumonia (3.0%), pleural effusion		
(1.7%), pneumonitis (1.6%), dyspnea		
(1.6%) and pulmonary embolism (1.5%)] *		
number of patients treated in compliance	80 %	61.4 – 92.3
with protocol / Feasibility of resection and		
early stopping rule [#]		
Radiologic response (CR or PR) per	10 %	2.1 – 26.5
RECIST 1.1 §		
Pathologic response (grade IIb or higher as	43 %	25.2 - 62.3
per Junker criteria) [§]		
* See also section 1.2.4 and IB of pembrolizur	nab	1

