2.4 Blinding and Randomization

As it is an open-label and single arm study, principles of blinding and randomization are not applicable.

2.5 **Descriptive Analyses**

- Descriptive analyses of continuous variables (summary statistics) will be described with the number of nonmissing observations, arithmetic mean, standard deviation (±SD), median, quartiles (Q1 and Q3) and range (minimum and maximum).
- Categorical variables (frequency statistics) will be described with the number of non-missing observations and percentages (%).

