5.3 Inferential Analysis

No statistical tests are performed due to the small sample size.

DFS and OS will be described by means of Kaplan-Meier method. Estimates of median DFS and OS rates for specific time points (at e.g. 12, 24 and 36 months) will be provided with the associated 95% confidence limits.

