6.2.3 Inferential Analysis

AE summary tables will provide the number and percentage of patients with AEs and the 95 % confidence intervals for the event rates according to Wilson.

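### The SAP defines no responder rate (CR/PR; Junker grade IIb/III), plans no confidence interval for either, and refers to a missing-response rule that is not there

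*SAP*

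**What the plan says.** Antitumor activity is part of the primary objective, and RECIST response rates and Junker regression grading are listed under the primary endpoint (Protocol 2.1 and 2.4; SAP 1.1.1 and 1.3.1).

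Protocol 8.2 states that "No formal sample size estimation has been performed", and adds that "The degree of the potential evidence provided by a sample size of N=30 is summarized in Table 3". Table 3 gives exact 95% intervals for eight rates. Two of them are efficacy rates, both dichotomised: CR or PR per RECIST at 10% (2.1–26.5), and "Pathologic response (grade IIb or higher as" per the Junker criteria at 43% (25.2–62.3). Protocol Appendix 3 likewise groups grades IIb and III as indicating good response.

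The SAP deals with response as follows:

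- **Outputs.** Section 5.1 and Tables 14.3.1 and 14.3.2 give overall response, change in tumor size and "Tumor regression grading stage". They are produced for the PP population first and repeated for ITT.
- **Summary method.** Under 2.5, "Categorical variables (frequency statistics) will be described with the number of non-missing observations and percentages".
- **Definitions.** Section 5.2 covers DFS, OS, incomplete dates and change in tumor size. It does not define a responder.
- **Efficacy inference.** Under 5.3, "No statistical tests are performed due to the small sample size". 95% limits are planned for DFS and OS only.
- **Safety inference.** Section 6.2.3 plans "95 % confidence intervals for the event rates according to Wilson", which applies to AEs only.
- **Missing data.** Section 2.8 restricts analysis to available data and lists exceptions. One exception is response rates, whose missing assessments are to be handled by a rule in Section 5.2. That rule is not in Section 5.2.

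**The concern.** AE rates and the secondary survival endpoints get intervals, while the primary efficacy rates get none. With about 30 patients, a response percentage without an interval says little about what the trial has shown.

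The second gap concerns the denominator. Under Protocol 3.1, a patient who progresses or has intolerable toxicity during immunotherapy goes to the end-of-treatment visit and then to follow-up, so there is no specimen to grade. The plan expects some such patients: feasibility is declared at 80% or more successful resections (Protocol 8.1). These patients are likely to be poor responders. If the percentage is taken over graded specimens, they leave it and the reported rate rises. Repeating the table for ITT does not cure this if ungraded ITT patients are still left out.

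The protocol's own reference result, from the neoadjuvant nivolumab pilot study, is stated over all treated subjects with an interval (9/21; Protocol 1.3). A percentage of graded specimens would be on a different basis.

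**Working it through.** **Inputs.** N = 30 and the reference rates of 43% and 10% come from Protocol 8.2, Table 3. The 80% feasibility level comes from Protocol 8.1. The responder counts and the numbers of graded patients below are assumptions, not trial results.

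**Formula.** The exact (Clopper-Pearson) 95% limits for x responders out of n are:

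- lower = 2.5% quantile of Beta(x, n − x + 1)
- upper = 97.5% quantile of Beta(x + 1, n − x)

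**Step 1: reproduce the plan's figures.**

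- Pathologic response: x = 0.43 × 30 = 12.9 gives 25.2–62.3, as printed. The whole number 13 gives 25.5–62.6, so the table used a fractional count.
- Radiologic response: x = 0.10 × 30 = 3 gives 2.1–26.5, as printed.
- The other rows of Table 3 also match to one decimal.
- The detection limit in 8.2 ("events with an incidence rate p > 9.5% will be observed at least once with a 95% probability"): 1 − (1 − 0.095)^30 = 0.9499, and solving for 95% gives p = 1 − 0.05^(1/30) = 9.503%. It reproduces.

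The planning figures are therefore sound. The intervals are wide: 62.3 − 25.2 = 37.1 points for pathologic response and 26.5 − 2.1 = 24.4 points for radiologic response.

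**Step 2: vary the denominator with the responders held fixed.** The lower case, 24 patients, is 0.80 × 30, the smallest number still meeting the feasibility criterion. The middle case, 27, is a further assumption.

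| Denominator | 13 responders (IIb/III), exact 95% CI | 3 responders (CR/PR), exact 95% CI |
|---|---|---|
| 30 (all) | 43.3% (25.5–62.6) | 10.0% (2.1–26.5) |
| 27 assessed | 48.1% (28.7–68.1) | 11.1% (2.4–29.2) |
| 24 assessed | 54.2% (32.8–74.4) | 12.5% (2.7–32.4) |

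The pathologic rate moves by 48.1 − 43.3 = 4.8 points with three ungraded patients, and by 54.2 − 43.3 = 10.9 points with six. The direction is fixed: for a given number of observed responders, a smaller denominator can only raise the rate.

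**Step 3: does the choice of interval matter?** Wilson limits, the SAP's method for AE rates, are 27.4–60.8 for 13/30 and 3.5–25.6 for 3/30, against exact limits of 25.5–62.6 and 2.1–26.5. The difference is small, but the method should be named in advance, and only the exact one matches Table 3.

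**The case against.** The best defence is that the SAP follows the protocol. The pathologic endpoint is a grade rather than a IIb/III rate, Protocol 8.4.1 and 8.4.3 plan frequencies and percentages, and the design is descriptive. Neither document promises an interval for response. That stands: this is a gap in the plan, not a broken commitment. It does not make the gap harmless. Omitting tests is no reason to omit intervals, which are estimation and which the SAP provides elsewhere. SAP 2.14, which lists departures from the protocol, records no decision to leave them out.

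A reader might infer more than the documents support:

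- **That the rates are never estimated, or cannot be set against the 43% reference.** All categories are tabulated, so each responder count is the sum of two cells, and anyone given N can compute a rate and an interval. What is missing is a prespecified rate, denominator and interval.
- **That patients vanish from the record.** Listing 16.2.3.5 shows whether grading was done and why not, and Listing 16.2.4.16 shows whether surgery was performed.
- **That the SAP fixes the percentage base as graded specimens.** Section 2.5 promises the non-missing count and a percentage but does not name the divisor. Section 2.8 intended a special rule for response rates, though it does not say whether Junker grading is covered. The shrinking denominator follows from the available-data default once that rule is found to be absent.
- **That Table 3 justified N=30.** The protocol disclaims a formal calculation and cites ethical, clinical and scientific grounds. Six of the table's eight rows concern adverse events or feasibility. Table 3 describes precision; it did not set N.

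**Conclusion.** The point holds in this form: two rates belonging to the primary endpoint have no SAP definition and no planned interval, and the rule for missing response assessments is promised in 2.8 but absent from 5.2. As written, the denominator is left open, and the default favours a higher pathologic response rate.

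In the illustration the denominator alone moves the pathologic rate by about 5 points (27 graded) to about 11 points (24 graded). These shifts assume 30 ITT patients, 13 responders, and ungraded patients who contribute no responders. If everyone is resected and graded, the shift is zero and only the missing intervals remain. Those are about 37 points wide for pathologic response and 24 for radiologic response at Table 3's reference rates.

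**What to change.** 1. **SAP 5.2, definitions.** Define pathologic response as Junker grade IIb or III and radiologic response as CR or PR at the pre-surgery assessment. Appendix 3 separates IIa from IIb at more or less than 10% vital tumor, so state where exactly 10% falls.
2. **SAP 5.2, missing assessments.** Supply the rule that 2.8 refers to, and say that it covers both rates.
3. **ITT repeats of Tables 14.3.1 and 14.3.2.** Report n/N over all ITT patients, counting unresected or unassessed patients as non-responders, with an exact (Clopper-Pearson) 95% CI to match Table 3.
4. **PP versions of the same tables.** Report the same rates and intervals over the PP population.
5. **Supplementary line.** Show the pathologic rate over graded specimens, labelled as such.
6. **SAP 5.3.** Name the interval method and add the two rates to the list of estimates given with 95% limits.

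The cost is two derived variables and a few table lines, with no new data. Counting unassessed patients as non-responders is a choice the documents do not prescribe. Its small downside is a somewhat lower, more conservative rate, and the supplementary line lets the reader see the difference.
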